### **Subjects with Suspected PTLD**

CNS imaging and/or neurologic consultation should be considered for any subject with a new or worsening neurologic finding. For subjects who undergo biopsy for suspicion of PTLD, the biopsy specimen will be evaluated for CD3, CD20, CD79 and EBER. Management of belatacept and other immunosuppressants in subjects with suspected PTLD should be discussed with the BMS Medical Monitor. BMS should be informed of all confirmed cases of PTLD.

## **6.6 Efficacy Assessments**

### **6.6.1 Primary Efficacy Assessment**

The primary endpoint is the incidence of donor-specific allo-antibody formation in patients treated with belatacept vs standard of care arm. Serum samples from study subjects will be evaluated periodically (see table 6.1) for the presence of donor-specific alloantibody using standard flow cytometric techniques.

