|--|-----------|------------------------|----------|----------|----------|----------|----------|----------|----------|----------|----------|----------|----------|-----------------|----------|----------|----------|----------|----------|----------|----------|--------|
| Visit #                                  | Screening | Initiation of Dialysis | 1        | 2        | 3        | 4        | 5        | 6        | 7        | 8-9      | 10       | 11-12    | 13       | 14-18           | 19       | 20-24    | 25       | 26-30    | 31       | 32-36    | 37       |        |
| time points                              |           |                        | 2 wks    | 1 mo     | 2mo      | 3mo      | 4mo      | 5mo      | 6mo      | 7-8mo    | 9mo      | 10-11 mo | 12 mo    | 13-17 mo        | 18 mo    | 19-23 mo | 24 mo    | 25-29 mo | 30 mo    | 31-35 mo | 36 mo    |        |
|  |           |                        | ± 2 days | ± 5 days | ± 5 days | ± 5 days | ± 5 days | ± 5 days | ± 5 days | ± 5 days | ± 5 days | ± 5 days | ± 5 days | ± 5 days        | ± 5 days | ± 5 days | ± 5 days | ± 5 days | ± 5 days | ± 5 days | ± 5 days |        |
| Eligibility Assessments           |           |                        |          |          |          |          |          |          |          |          |          |          |          |                 |          |          |          |          |          |          |          |        |
| Informed Consent                         | X         |                        |          |          |          |          |          |          |          |          |          |          |          |                 |          |          |          |          |          |          |          |        |
| Inclusion/Exclusion Criteria             | X         |                        |          |          |          |          |          |          |          |          |          |          |          |                 |          |          |          |          |          |          |          |        |
| Medical History                          | X         |                        |          |          |          |          |          |          |          |          |          |          |          |                 |          |          |          |          |          |          |          |        |

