| Safety Assessments                |           |                        |          |          |          |          |          |          |          |          |          |          |          |                 |          |          |          |          |          |          |          |        |
| Physician Visit                          | X         | X                      |          |          | X        | X        | X        | X        | X        |          | X        |          |          |                 | X        |          |          |          | X        |          | X        |        |
| Physical Examination                     | X         | X                      |          | X        | X        | X        | X        | X        | X        |          | X        |          | X        |                 | X        |          | X        |          | X        |          | X        |        |
| Vital Signs                              | X         | X                      |          | X        | X        | X        | X        | X        | X        | X        | X        | XX       | X        | XXXXXX          | X        | XXXXXX   | X        | XXXXXX   | X        | XXXXXX   | X        | XXXXXX |
| Assessment of Signs and Symptoms         |           | X                      | X        | X        | X        | X        | X        | X        | X        | X        | X        | XX       | X        | XXXXXX          | X        | XXXXXX   | X        | XXXXXX   | X        | XXXXXX   | X        | XXXXXX |
| Adverse Events Assessments               |           | X                      | X        | X        | X        | X        | X        | X        | X        | X        | X        | XX       | X        | XXXXXX          | X        | XXXXXX   | X        | XXXXXX   | X        | XXXXXX   | X        | XXXXXX |
| Laboratory Tests                         | X         | X                      |          | X        | X        | X        | X        | X        | X        |          | X        |          | X        |                 | X        |          | X        |          | X        |          | X        |        |
| EBV/CMV titer                            | X         | X                      |          | X        |          | X        |          |          | X        |          |          |          | X        |                 | X        |          | X        |          | X        |          | X        |        |

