| Neurologic Evaluation                    | X         | X                      |          |          |          | X        |          |          |          |          | X        |          | X        |                 | X        |          | X        |          | X        |          | X        |        |
| Efficacy Assessments              |           |                        |          |          |          |          |          |          |          |          |          |          |          |                 |          |          |          |          |          |          |          |        |
| DSA/PRA                                  | X         | X                      |          |          | X        | X        | X        | X        | X        |          |          |          | X        |                 |          |          | X        |          | X        |          | X        |        |
| Mechanistic                       |           |                        |          |          |          |          |          |          |          |          |          |          |          |                 |          |          |          |          |          |          |          |        |
| Sample storage                           | X         | X                      |          | X        | X        | X        | X        | X        | X        | X        | X        | XX       | X        | X  |          | XXXXXX   | X        | XXXXXX   | X        | XXXXXX   | X        | XXXXXX |
| Clinical Drug Supplies            |           |                        |          |          |          |          |          |          |          |          |          |          |          |                 |          |          |          |          |          |          |          |        |
| Randomization                            |           | X                      |          |          |          |          |          |          |          |          |          |          |          |                 |          |          |          |          |          |          |          |        |
| MMF weaning                  |           | X                      | X        |          |          |          |          |          |          |          |          |          |          |                 |          |          |          |          |          |          |          |        |

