## 6.1

| Standard of Care Post-Dialysis |        |                        |          |          |          |          |          |          |          |          |          |          |          |          |          |          |
|---------------------------------------|--------|------------------------|----------|----------|----------|----------|----------|----------|----------|----------|----------|----------|----------|----------|----------|----------|
| Visit #                        |        | Initiation of Dialysis | 2        | 3        | 4        | 5        | 6        | 7        | 8        | 9        | 10       | 11       | 12       | 13       | 14       | 15       |
| time points                    | Screen |                        | 1mo      | 2mo      | 3mo      | 4mo      | 5mo      | 6mo      | 9mo      | 12mo     | 15mo     | 18mo     | 21mo     | 24mo     | 30mo     | 36mo     |
|                                       |        |                        | ± 5 days | ± 5 days | ± 5 days | ± 5 days | ± 5 days | ± 5 days | ± 5 days | ± 5 days | ± 5 days | ± 5 days | ± 5 days | ± 5 days | ± 5 days | ± 5 days |
| Eligibility Assessments        |        |                        |          |          |          |          |          |          |          |          |          |          |          |          |          |          |
| Informed Consent                      | X      |                        |          |          |          |          |          |          |          |          |          |          |          |          |          |          |
| Inclusion/Exclusion Criteria          | X      |                        |          |          |          |          |          |          |          |          |          |          |          |          |          |          |
| Medical History                       | X      |                        |          |          |          |          |          |          |          |          |          |          |          |          |          |          |
| Safety Assessments             |        |                        |          |          |          |          |          |          |          |          |          |          |          |          |          |          |

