| Physician Visit                       | X      |                        | X        | X        | X        | X        | X        | X        | X        | X        | X        | X        | X        | X        | X        | X        |
| Physical Examination                  | X      |                        | X        | X        | X        | X        | X        | X        | X        | X        | X        | X        | X        | X        | X        | X        |
| Vital Signs                           | X      |                        | X        | X        | X        | X        | X        | X        | X        | X        | X        | X        | X        | X        | X        | X        |
| Assessment of Signs and Symptoms      | X      |                        | X        | X        | X        | X        | X        | X        | X        | X        | X        | X        | X        | X        | X        | X        |
| Adverse Events Assessments            | X      |                        | X        | X        | X        | X        | X        | X        | X        | X        | X        | X        | X        | X        | X        | X        |
| Laboratory Tests                      | X      |                        | X        | X        | X        | X        | X        | X        | X        | X        | X        | X        | X        | X        | X        | X        |
| EBV/CMV titer                         |        |                        |          |          |          |          |          |          |          |          |          |          |          |          |          |          |
| Neurologic Evaluation                 | X      |                        |          |          | X        |          |          | X        |          | X        |          | X        |          | X        | X        | X        |
| Efficacy Assessments           |        |                        |          |          |          |          |          |          |          |          |          |          |          |          |          |          |
| DSA/PRA                               | X      |                        | X        | X        | X        | X        | X        | X        | X        | X        | X        | X        | X        | X        | X        | X        |

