| Mechanistic                    |        |                        |          |          |          |          |          |          |          |          |          |          |          |          |          |          |
| Sample Storage                        | X      |                        | X        | X        | X        | X        | X        | X        | X        | X        | X        | X        | X        | X        | X        | X        |
| Clinical Drug Supplies         |        |                        |          |          |          |          |          |          |          |          |          |          |          |          |          |          |
| Randomization                         | X      |                        |          |          |          |          |          |          |          |          |          |          |          |          |          |          |
| Tac/CsA weaning          | X      |                        |          |          |          |          |          |          |          |          |          |          |          |          |          |          |
| MMF weaning              |        | X                      | X        |          |          |          |          |          |          |          |          |          |          |          |          |          |
| Prednisone weaning       |        |                        | X        | X        | X        |          |          |          |          |          |          |          |          |          |          |          |

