## Table 6.1

### SOE footnotes

-  Belatacept dose 10 mg/kg IV administered at study day 0, week 2, month 1, 2, 3
-  Belatacept dose 5 mg/kg IV q month administered beginning study month 4 and continuing through end of study treatment period
-  Infusion dose based on subject's actual body weight at enrollment and will not be modified during the course of the study unless there is a change of body weight greater than  $\pm 10\%$
-  at first dose of belatacept, reduce CNI or mTOR inhibitor dose by 50%
-  at second dose of belatacept (week 2) discontinue CNI or mTOR inhibitor
-  Continue concomitant immunosuppression (MMF/MPA/AZA and/or prednisone) at current dose until initiation of dialysis
-  Decrease MMF/MPA/AZA dose by 50% at initiation of dialysis. Discontinue MMF/MPA/AZA 2 weeks after initiation of dialysis
-  Reduce prednisone dose by 50% one month after initiation of dialysis, by half again at 2 months after initiation of dialysis. Discontinue prednisone at 3 months after initiation of dialysis
-  After initiation of hemodialysis, infusion visits will be scheduled on non-dialysis days
-  Maintain target tacrolimus trough of 3-5 ng/ml (or equivalent CNI or mTOR inhibitor trough) until initiation of dialysis
-  Continue concomitant immunosuppression (MMF/MPA/AZA and/or prednisone) at current dose until initiation of dialysis
-  Discontinue CNI or mTOR inhibitor over 5 days after initiation of dialysis
-  Decrease MMF/MPA/AZA dose by 50% at initiation of dialysis. Discontinue MMF/MPA/AZA 2 weeks after initiation of dialysis
-  Reduce prednisone dose by 50% one month after initiation of dialysis, by 50% again at 2 months after initiation of dialysis. Discontinue prednisone at 3 months after initiation of dialysis

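### After dialysis starts, Table 6.1 tests the belatacept arm for donor-specific antibody less often than the control arm, and it fixes no sample at month 36 from randomization

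*Combined protocol and SAP*

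**What the plan says.** Section 6.6.1 defines the primary assessment and defers its timing: "Serum samples from study subjects will be evaluated periodically (see table 6.1) for the presence of donor-specific alloantibody using standard flow cytometric techniques". Sections 2.1 and 8.2 set the endpoint at 36 months after randomization, and Section 4.1 plans follow-up of the same length.

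Table 6.1 has four grids. In both pre-dialysis grids DSA/PRA is marked at screening and months 0, 1, 2, 3, 6, 9, 12, 18, 24, 30 and 36. The post-dialysis grids count visits from initiation of dialysis and differ by arm:

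- **Belatacept.** The time points after initiation and week 2 run "1 mo | 2mo | 3mo | 4mo | 5mo | 6mo | 7-8mo | 9mo | 10-11 mo | 12 mo" and on to month 36. The DSA/PRA row begins "DSA/PRA | X | X | | | X | X | X | X | X | | | | X". Matched to its header, it is marked at screening, initiation, and months 2, 3, 4, 5, 6, 12, 24, 30 and 36.
- **Standard of care.** The grid has separate columns at "12mo | 15mo | 18mo | 21mo | 24mo". Its DSA/PRA row begins "DSA/PRA | X | | X | X | X | X | X | X | X | X | X" and is marked at every visit after initiation: months 1-6, 9, 12, 15, 18, 21, 24, 30 and 36.

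Nothing gives a subject who starts dialysis on study a DSA sample at month 36 from randomization. Section 6.1 brings assessments forward only on withdrawal. The reduced follow-up in Section 7.7 collects survival, dialysis status and serious adverse events, not DSA. The banked blood in Section 6.3 is optional and kept for mechanistic work.

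**The concern.** An antibody that forms between visits is dated at the next visit. It is not counted if no test follows before month 36, or if it has gone by the next test. Testing one arm less often therefore lowers that arm's observed proportion (chi-squared) and delays its event dates (log-rank), with no drug effect needed. Here the sparser schedule belongs to the experimental arm, so the bias favors the study hypothesis. No reason for the difference is given.

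The clock adds a second problem. Once a subject moves to the post-dialysis grid, a DSA test falls at month 36 from randomization only if the dialysis start date happens to line up. Subjects already on dialysis at enrollment are not affected, because their two clocks coincide.

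**Working it through.** **Two readings of the belatacept post-dialysis row.** In the other three grids the DSA/PRA row equals the Laboratory Tests row. In this grid the laboratory row begins "Laboratory Tests | X | X | | X | X | X | X | X | X | | X" and is marked at months 1, 9 and 18, where DSA/PRA is blank. Those three blanks may be lost marks. Each belatacept figure below is as printed, then [with months 1, 9 and 18 restored]. Months 15 and 21 are control-only on either reading.

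**Tests after month 6 through month 24.** Control: 9, 12, 15, 18, 21, 24 = 6. Belatacept: 12, 24 = 2 [9, 12, 18, 24 = 4]. Longest gap: 3 months against 12 [6].

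**Mean wait from onset to next test**, for onset uniform over the window = sum of (gap²/2) / window length:

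| Months after dialysis | Control | Belatacept |
|---|---|---|
| 0-6 | 6(1/2)/6 = 0.5 | (2 + 4(1/2))/6 = 0.7 [0.5] |
| 6-24 | 6(9/2)/18 = 1.5 | (18 + 72)/18 = 5.0 [(4.5 + 4.5 + 18 + 18)/18 = 2.5] |
| 24-36 | (18 + 18)/12 = 3.0 | 3.0 [3.0] |

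**Month 36 from randomization.** For dialysis starting at whole month d = 1 to 35, a test falls at month 36 when 36 − d is a marked month: 13 of 35 starts on control, 8 [11] on belatacept. With continuous start dates, only about 8-12% of starts have a test within 5 days of month 36.

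**Detection by month 36 at equal hazards, persistent DSA.** Section 8.3.3 gives a control hazard of 0.02545 per month. It reproduces: −ln(1 − 0.60)/36 = 0.02545. Apply it to both arms. Detection is 1 − exp(−0.02545 t), where t is the last test at or before month 36.

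- Worst case, dialysis at month 13. Control: t = 13 + 21 = 34, 57.9%. Belatacept: t = 13 + 12 = 25, 47.1% [t = 13 + 18 = 31, 54.6%].
- Starts at months 13-21: 59.0% against 52.1% [56.8%].
- All starts at months 0-35, equally weighted: 58.6% against 56.6% [58.0%]. The mean blind period before month 36 is 1.3 against 3.1 [1.8] months. The last in-window test coincides for 23 [30] of the 36 starts.

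**Simulation at equal hazards.** The same 600,000 subjects per scenario were read under each grid, with exponential time to dialysis of assumed median 6 to 24 months. Monte Carlo SE of a difference is about 0.03 points.

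| DSA duration (assumed) | Spurious difference, points |
|---|---|
| Persistent | 1.2-1.6 [0.3-0.4] |
| Mean 12 months | 2.9-5.5 [0.7-1.5] |
| Mean 6 months | 3.5-7.4 [0.9-2.2] |

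If dialysis starts are uniform over months 1-24, the persistent figure is 2.7 [0.8]. If all DSA arises within 6 months of dialysis (assumed in 65% of subjects, onset uniform), it is at most 0.1 persistent and 0.6-1.5 transient [0.0 for both].

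**False findings in favor of belatacept**, 36 per arm, 10,000 trials, nominal 2.5%, SE about 0.16 points:

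| | Chi-squared | Log-rank |
|---|---|---|
| Persistent | 2.8-3.2% [2.2-2.5%] | 3.5-3.8% [2.6-3.0%] |
| Mean 6 months | 4.7-8.9% [2.9-3.4%] | 4.9-8.5% [3.1-3.7%] |
| With the fix | 2.3-2.8% | 2.4-2.8% |

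**The case against.** The belatacept post-dialysis grid is visibly damaged. It carries an extra unlabelled last column and some six-mark entries in five-visit columns, and its Physician Visit row is blank at months where Physical Examination is marked. Four against six is then the safer count. On that reading, with persistent DSA, the spurious difference is 0.3-0.4 points, when one subject in an arm of 36 is 100/36 = 2.8 points. The error rates are close to nominal with or without the fix. The larger figures need real blanks and also antibody that disappears, and the documents establish neither. Section 1.4 ties sensitization to stopping immunosuppression at dialysis, which suggests onset in the early months, when testing is nearly equal. At the plan's own belatacept hazard of 0.00619, under-detection with persistent DSA is only 0.6-0.7 points [0.1-0.2]. The month-36 gap affects both arms, and the whole-month counts exaggerate the difference between them. The blank control cell at initiation may be a column shift: the same grid prints "Tac/CsA weaning 12 | X" under Screen, whereas footnote 12 reads "Discontinue CNI or mTOR inhibitor over 5 days after initiation of dialysis".

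Most of this stands as a limit on size. It does not remove the two control-only visits, which survive either reading, or the missing month-36 sample. Continuous start dates narrow the difference between arms at month 36 but leave fewer subjects with a sample there.

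**Conclusion.** The concern holds and should be fixed; confidence is moderate. As written, the schedule tests the experimental arm less often for the primary endpoint after dialysis (2 [4] tests against 6 after month 6 through month 24) and leaves most on-study dialysis starters without a sample at the endpoint time. The direction favors belatacept. Against a planned 40-point effect the bias is small if DSA persists, close to nil if the marks were also lost, and larger only if DSA is transient. The size rests on assumed times to dialysis and DSA duration, neither of which the documents give, and on which reading of the damaged grid is right. If the control initiation cell is really marked, the difference grows by at most 0.1 points (persistent) or 0.3-0.4 points (mean 6 months). The point does not invalidate the trial; it is an avoidable objection to its primary result.

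**What to change.** 1. Check the post-dialysis DSA/PRA cells, including the control initiation cell, against the source table.
2. Use one post-dialysis DSA/PRA schedule in both arms. Add months 15 and 21 to the belatacept grid, and months 1, 9 and 18 if they are truly blank.
3. Require a DSA/PRA sample at initiation of dialysis and at 36 months from randomization in both arms. Steps 2 and 3 are both needed. With median time to dialysis of 12 months, a month-36 sample alone removes the persistent-DSA difference but leaves 3.3-4.8 points [0.8-1.3] if DSA lasts a mean of 12 or 6 months.
4. If samples have already been missed, first test the optional banked blood drawn every 3 months after dialysis, where consent and sample type allow. Keep an analysis restricted to common time points as a sensitivity analysis only.

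**Cost.** A table edit; two to five extra assays per belatacept subject at monthly infusion visits that already take place; a control initiation sample if it is truly absent; and one month-36 sample where no visit falls, which for some control subjects means a shifted or extra visit.

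**Limit.** Pre- and post-dialysis grids would still differ. If belatacept delays dialysis (assumed median 24 against 12 months), about 0.1 points (persistent) or 1.4 points (mean 6 months) remains.
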